4.10.4. Vital Signs and Other Physical Findings

Vital signs and physical characteristics include systolic blood pressure, diastolic blood pressure, pulse, weight, body mass index, and body temperature. Original-scale data will be analyzed. The planned analyses described for the laboratory analytes in Section 4.10.3 will be used to analyze the vital signs and physical characteristics. Unless otherwise specified, the planned summaries of AEs will be provided for the treatment period. The criteria for identifying subjects with treatment-emergent abnormalities are based on Table 4.4.

Table 4.4. Categorical Criteria for Abnormal Treatment-Emergent Blood Pressure and Pulse Measurement, and Categorical Criteria for Weight and Temperature Changes for Adults

Parameter	Low	High
	≤90 (low limit) and decrease from	≥140 (high limit) and increase from
Systolic BP (mm Hg)	lowest value during baseline ≥20 if >90	highest value during baseline ≥20 if
580 581 5850 4	at each baseline visit	<140 at each baseline visit
	≤50 (low limit) and decrease from	≥90 (high limit) and increase from
Diastolic BP (mm Hg)	lowest value during baseline ≥10 if >50	highest value during baseline ≥10 if <90
75 85837	at each baseline visit	at each baseline visit
	<50 (low limit) and decrease from	>100 (high limit) and increase from
Pulse (beats per minute)	lowest value during baseline ≥15 if ≥50	highest value during baseline ≥15 if
	at each baseline visit	≤100 at each baseline visit
Wainht (Ira)	(Loss) decrease ≥7% from lowest value	(Gain) increase ≥7% from highest value
Weight (kg)	during baseline	during baseline
	<96 (low limit) and decrease from	≥101 (high limit) and increase from
Temperature (°F)	lowest value during baseline ≥2 if ≥96 at	highest value during baseline ≥2 if <101
	each baseline visit	at each baseline visit

Abbreviations: BP = blood pressure.

4.10.5. Depression and Suicide

During the study, suicidal ideation and behavior, and depression will be assessed prospectively by the investigator via signs and symptoms and using QIDS-SR16 and the C-SSRS.

4.10.5.1. Symptoms of Depression 16-Item Quick Inventory of Depressive Symptomatology-Self Report (QIDS-SR16)

The QIDS-SR16 (Rush et al. 2003) is a 16-item, self-report instrument intended to assess the existence and severity of symptoms of depression as listed in the American Psychiatric Association's *Diagnostic and Statistical Manual of Mental Disorders*, 4th Edition (APA 1994). Patients are asked to consider each statement as it relates to the way they have felt for the past 7 days. There is a unique 4-point ordinal scale for each item, with scores ranging from 0 to 3 reflecting increasing depressive symptoms as the item score increases. The QIDS-SR16 total score is derived as the sum of the scores across the 9 scale domains. For scale domains that contain more than 1 item, the domain score is the highest item rating given across the items within that domain:

- Sleep: the highest score on any 1 of the 4 sleep items (Items 1 to 4)
- Depressed mood: Item 5

• Weight/appetite change: the highest score on any 1 of the 4 weight items (Items 6 to 9)

Concentration: Item 10

Worthlessness/Guilt: Item 11
Suicidal ideation: Item 12
Decreased interest: Item 13
Decreased energy: Item 14

 Psychomotor changes: the highest score on either of the 2 psychomotor items (Items 15 and 16)

In the presence of missing data, the following rules will be employed to derive the total score. Firstly, considering the 3 multi-item domains (sleep, weight/appetite change, and psychomotor change), the domain score should be based on the maximum value across the appropriate items, and it should be missing only if each item is missing. Further, considering the 9 domain scores, the total score should be derived as missing if there are 3 or more domains that are missing; if 1 or 2 domain scores are missing, then the total score should be derived using a total score that is prorated to the full scale range (0 to 27) based on the available domain scores, retaining 1 decimal place in the total score derived in the presence of missing data.

The QIDS-SR16 total scores will also be categorized in the severity classes shown in Table 4.5.

Table 4.5. Severity of Depressive Symptoms Categories Based on the QIDS-SR16 Total Score

QIDS-SR16 Severity of Depressive Symptoms Category	QIDS-SR16 Total Score
0 = None	0-5
1 = Mild	6-10
2 = Moderate	11-15
3 = Severe	16-20
4 = Very Severe	21-27

Abbreviations: QIDS-SR16 = Quick Inventory of Depressive Symptomatology Self Report.

Treatment differences in mean change in the QIDS-SR16 total score will be analyzed using the linear regression method described in Section 4.2. Only visits that occur on or before the date the participant discontinued treatment will be included in the analysis.

Using the QIDS-SR16 Severity of Depressive Symptoms categories shown in Table 4.5, shift tables will be used to show the number and percentage of participants in each category based on the QIDS-SR16 Total Score at every postbaseline visit in contingent to the baseline. Further summarization of change from baseline in severity using categories of any improvement, no change, and any worsening, by treatment conditions may also be tabulated.

The number and percentage of participants with treatment-emergent changes in QIDS-SR16 total score severity categories at any time during the treatment period, based on any increase to mild and above, moderate or above, severe or above, very severe, will also be summarized.

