8.2.10. Suicidal Ideation and Behavior Risk Monitoring

Participants should be monitored appropriately and observed closely for suicidal ideation and behavior or any other unusual changes in behavior, especially at the beginning and end of the course of study intervention. Participants who have signs of suicidal ideation or behavior should be considered for discontinuation of study intervention, following a risk assessment (see Section 7.1). See Section 8.3.1.1 for timing of AE collection relative to collection of the C-SSRS.

At screening, suicidal ideation and behavior and depressive symptomatology will be assessed by use of the

- · C-SSRS, and
- QIDS-SR16

See the SoA of the relevant ISA for assessments in the treatment and posttreatment follow-up periods.

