4.10.3. Clinical Laboratory Evaluations

All laboratory tests will be presented using the Système International of units (SI) and United States conventional (CN) units. For topics of safety in special groups and circumstances, laboratory test units will be specified for each analysis. Central laboratory reference ranges will be used.

The following will be conducted for laboratory analyte measurements collected quantitatively:

Box plots for observed values

Values at each visit (starting at randomization) and change from baseline to each visit and to last postbaseline measure will be displayed in box plots for patients who have a baseline and at least 1 postbaseline visit. For visits included in the treatment period, patients will be included only if the visit occurs on or before the date of treatment discontinuation or completion. The follow-up visit will be the first visit that occurred during the follow-up period. Individual measurements outside of the reference limits will also be displayed using distinct symbols overlaying the box plot. Original-scale data will be used for the display but for some analytes (for example, immunoglobulins) a logarithmic scale will be used to aid in viewing measures of central tendency and dispersion. Unplanned measurements will be excluded. Descriptive summary statistics will be included in a table below the box plot. These box plots will be used to evaluate trends over time and to assess the potential impact of outliers on central tendency summaries. No inferential statistics will be provided.

• Treatment-emergent high/low analyses

The number and percentage of patients with treatment-emergent high and low laboratory results at any time will be summarized by treatment conditions. Planned and unplanned measurements will be included. A treatment-emergent high result is defined as a change from a value less than or equal to the high limit at all baseline visits, to a value greater than the high limit at any time

during the treatment period, and up to 60 days after treatment discontinuation. A treatmentemergent low result is defined as a change from a value greater than or equal to the low limit at all baseline visits, to a value less than the low limit at any time during the treatment period, and up to 60 days after treatment discontinuation. No inferential statistics will be provided.

Listing of abnormal findings

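### The QIDS-SR16 category-worsening count has no post-treatment window, so depressive worsening after the treatment period may not be counted by arm

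*SAP*

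**What the plan says.** SAP 4.10.5.1 plans three kinds of QIDS-SR16 output, each with its own period.

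- **Mean change in total score.** This is the only output for which the section plans an analysis of treatment differences. The rule is "Only visits that occur on or before the date the participant discontinued treatment will be included in the analysis". The model is given as the "linear regression method described in Section 4.2".
- **Shift tables by severity category.** These are "based on the QIDS-SR16 Total Score at every postbaseline visit in contingent to the baseline". No end of the period is given.
- **Category worsening.** The count is of participants with "treatment-emergent changes in QIDS-SR16 total score severity categories at any time during the treatment period". No days are added after treatment.

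Protocol 8.2.10, the section that introduces both the C-SSRS and the QIDS-SR16, asks sites to watch for "suicidal ideation and behavior or any other unusual changes in behavior, especially at the beginning and end of the course of study intervention". For the timing of assessments after screening it says: "See the SoA of the relevant ISA for assessments in the treatment and posttreatment follow-up periods". SAP 4.3 likewise leaves the end of the treatment period to the ISAs. SAP 4.10 makes the master SAP's safety rules the default for every ISA unless the ISA says otherwise.

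**The concern.** The protocol names the end of the intervention course as a time for particular attention, and it expects follow-up visits after treatment. Yet the two QIDS-SR16 outputs with a stated period both end with treatment. A participant whose depressive symptoms move up a category at a follow-up visit would not be in the worsening count, and nothing in 4.10.5.1 clearly puts that participant into any by-arm figure.

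The other safety measures in the SAP have a stated reach beyond treatment, and no reason is given for treating this scale differently. At stake is a default for the whole platform. Each ISA inherits it unless its own plan overrides it, and the first ISA has only about 45 participants per arm, so a safety table built on few events could change with a handful of scores.

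**Working it through.** No arithmetic applies, because no sample size, power or event count depends on this rule. The check sets the stated windows side by side.

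| Output | Where | Reach beyond treatment |
|---|---|---|
| QIDS-SR16 mean change | SAP 4.10.5.1 | none; ends at the discontinuation date |
| QIDS-SR16 category worsening | SAP 4.10.5.1 | none; treatment period only |
| QIDS-SR16 shift tables | SAP 4.10.5.1 | not stated |
| C-SSRS | SAP 4.10.5.2 | listing by patient and visit, no cut-off |
| TEAEs | SAP 4.10.2.1 | 30 days after discontinuation; later AEs listed |
| SAEs | SAP 4.10.2.2 | treatment and follow-up periods |
| Treatment-emergent laboratory results | SAP 4.10.3 | "up to 60 days after treatment discontinuation" |
| Vital signs and weight | SAP 4.10.4 | use the analyses of 4.10.3 |
| Hepatic categories | SAP Table 4.3, analysis-period column | treatment and follow-up periods |

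The category-worsening count is the outlier: 0 days past the treatment period, against 30 for TEAEs and 60 for laboratory results.

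Next, what happens to individual scores:

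1. *Stops drug early, stays in the study, scored later within the treatment period.* The score is out of the mean change. It may be in the category count, because Protocol 7.1 strongly encourages such participants to remain through the treatment period and the count is bounded by that period, not by the stop date. Whether it is in depends on the ISA's definition of the period.
2. *Completes treatment, worsens at a follow-up visit.* The score is out of the category count. For mean change the rule is unclear: 4.10.5.1 mentions only discontinuation, whereas the box-plot rule in 4.10.3 names discontinuation or completion. Read literally, a completer's follow-up score could enter the mean change while an early stopper's could not.
3. *Either participant, in the shift table.* This depends on what postbaseline means. SAP 4.3 does not say when it ends. Protocol 9.3.5.1 takes the treatment period as the postbaseline period for AEs. On that reading the shift table also stops with treatment; on the plain reading it continues into follow-up.

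The clear gap is therefore case 2: category worsening first seen in follow-up. Case 1 depends on the ISA, and case 3 on an undefined term.

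The model reference also needs attention. The text of SAP 4.2 available here contains no linear regression method. One item in that section is not reproduced in this copy, so the sponsor should check it. The only model visible for QIDS-SR16 mean change is the optional ANCOVA with treatment and baseline in SAP 4.10. This is a clerical matter.

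**The case against.** The best defence has four parts.

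First, post-treatment mood is not unobserved. The shift tables as worded may include later visits, the C-SSRS listing has no cut-off, SAEs run into follow-up, and Protocol 9.3.5.1 plans a summary of follow-up emergent AEs. This stands against any inference that depression after stopping is left out altogether; the documents do not support that reading. The cover is partial, however. The C-SSRS listing concerns suicidality and self-injury rather than depression severity, it is not a by-arm count, and the shift-table period is unstated.

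Second, "especially at the beginning and end of the course of study intervention" is an instruction to sites on observing suicidality and behaviour, not an analysis window. That is right. A reader might infer that the SAP contradicts the protocol, and it does not. Visits up to and including the stop date also stay in the mean change. The instruction shows only why the period after treatment deserves a count.

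Third, an on-treatment mean change is the SAP's own convention: the laboratory displays in 4.10.3 restrict treatment-period visits in the same way. This stands, and the mean-change rule should stay. The same laboratory display does, however, also show a follow-up visit.

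Fourth, the ISA may override the rule, and it sets whether the scale is given in follow-up at all. This limits what can be claimed but does not remove the point, because these are the defaults.

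**Conclusion.** The point holds as a gap in the default analysis windows. The mean-change comparison and the category-worsening count have no post-treatment window, unlike the SAP's other safety measures, and the one output that might show later scores has no stated period. Worsening after the treatment period may not be counted by arm.

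The size cannot be determined. It depends on whether the ISA collects QIDS-SR16 in follow-up, where the ISA ends the treatment period, and whether the ISA SAP changes the rule. An estimate built on an assumed stopping rate would not follow either, since early stoppers' later scores can still fall within the treatment period and so within the category count.

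A reader might also infer a bias toward showing no harm. The documents do not support a direction. Mood could worsen after stopping, or it could recover if low mood were drug-related, in which case added scores would dilute a signal. SAP 4.10 also uses safety p-values mainly as a flag. This is a cheap improvement to the plan, not a demonstrated error in a result.

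**What to change.** In SAP 4.10.5.1:

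- Leave the mean change on-treatment, and word its cut-off as discontinuation or completion, as in 4.10.3.
- Extend the category-worsening count from first dose through follow-up, including any early termination visit, wherever the ISA schedules the scale. Show the treatment period and follow-up in separate columns.
- State the same period for the shift tables.
- Point the model reference to the ANCOVA in 4.10.

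The first score after stopping should not be moved into the on-treatment mean change. The scale asks about the past 7 days (Protocol 8.2.10.2), and with no limit on the delay such a score could be wholly off drug.

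The cost is SAP wording and one extra column. Nothing new is collected beyond what each ISA already schedules. The downside is that the follow-up count will contain some off-drug scores, so the column should be labelled accordingly.

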4.10.5.2. Columbia Suicide Severity Rating Scale (C-SSRS)

Suicidal ideation, suicidal behavior, and self-injurious behavior without suicidal intent, based on the C-SSRS, will be listed by patient and visit. Only patients that show suicidal ideation or behavior, or self-injurious behavior without suicidal intent, will be displayed (that is, if a patient's answers are all "no" for the C-SSRS, then that patient will not be displayed). However, if a patient reported any suicidal ideation or behavior or self-injurious behavior without suicidal intent at any time point, then all their ideation and behavior will be displayed, even if not positive.

4.11. Other Analyses

4.11.1. Concomitant Therapy

Previous and concomitant medications including corticosteroids, anti-malarials and immunosuppressants will be summarized for each ISA and will be presented by Anatomical Therapeutic Chemical (ATC) drug classes using the latest version of the World Health Organization (WHO) drug dictionary. Details can be found in Master Protocol IMMA Section 6.5 and each ISA-SAP.

To allow for assessments of changes in doses of various corticosteroids, all corticosteroid doses will be standardized to an equivalent prednisone dose. Table 4.6 provides a summary of frequent corticosteroids and their prednisone-equivalent dose. The dose of the drug listed in Column 1 of Table 4.6 is multiplied by the conversion factor in Column 2 to provide the prednisone equivalent dose (in milligrams). This dose of corticosteroid will be referred to as "prednisone (or equivalent)" throughout this document. See Appendix 1 for a complete table showing conversion factors for each corticosteroid medication identified during the study, instructions for selecting corticosteroids, and the manual review process.

A daily dose of corticosteroid will be derived using the prednisone-equivalent dose for each study day from baseline to the treatment discontinuation day for patients who discontinue treatment early, or to the day before for treatment completers. For immunosuppressant and antimalarial medications, a daily dose will be calculated for each medication by preferred name.

Table 4.6. Conversion Factors for Calculating Prednisone (or Equivalent)

Doses

Column 1	Column 2
Corticosteroid Preferred Term	Conversion Factor for Converting to an Equivalent Prednisone Dose
Prednisone	1
Prednisolone	1
Methylprednisolone	1.25
Triamcinolone	1.25
Cortisone	0.2
Hydrocortisone	0.25
Betamethasone	6.25
Dexamethasone	6.25
Paramethasone	2.5
Deflazacort	0.83

4.11.2. Treatment Compliance

Treatment compliance with the investigational product will be summarized by treatment for each ISA. Intervention-specific analyses are described in the respective ISAs.

4.11.3. Pharmacokinetics/Pharmacodynamics

Intervention-specific pharmacokinetic (PK)/pharmacodynamic (PD) analyses are described in the respective ISAs, in a separate PK/PD analysis plan, or in both.

4.11.4. Immunogenicity

When applicable, the frequency and percentage will be tabulated for each ISA for

- participants with preexisting antidrug antibodies (ADA), and
- participants with TE-ADA to the active study intervention.

A subject is evaluable if there is at least one non-missing test result for ADA for both the baseline period and the postbaseline period. All percentages are relative to the total number of ADA evaluable subjects. A TE-ADA evaluable subject is considered to be TE-ADA positive (TE-ADA+) if the subject has at least one postbaseline titer that is 2-fold (1 dilution) greater than the minimum required dilution if no ADAs were detected at baseline (treatment-induced ADA) or is a 4-fold (2 dilutions) increase in titer compared to baseline if ADAs were detected at baseline (treatment-boosted ADA). For the TE-ADA+ participants, the distribution of maximum titers will be described. If assessed, the frequency of neutralizing antibodies may also be tabulated in TE-ADA+ participants.

The relationship between the presence of antibodies and study intervention concentrations, and the PK parameters and PD response including safety and efficacy, may also be assessed. Additional details may be provided in the respective ISAs and ISA-SAPs.

4.11.5. Patient-Reported Outcomes

Intervention-specific analyses of patient-reported outcomes, if applicable, are described in the respective ISAs.

4.11.6. Subgroup analyses

Intervention-specific subgroup analyses are described in the respective ISAs.

4.13. Assessment Committee (AC) or Other Review Board

Eligibility Review Committee

An eligibility review committee, also called adjudication panel, will review study entry data to ensure that prospective study participants meet the study entry criteria, particularly SLE disease activity criteria, prior to random assignment. In addition, the committee will help ensure that high quality data are entered into the EDC system for lupus assessments. The committee may include members of a third-party organization, members of the study team, and external SLE consultants as needed. Membership, responsibilities, operations, and measures to maintain confidentiality will be described in a committee charter.

Assessment Committee (AC)

In addition to safety reviews routinely performed by the sponsor as described in Master Protocol IMMA Section 8.2, the AC will review the safety data in an unblinded fashion periodically, or on an ad hoc basis during the study, and will determine whether any changes (for example, dose reductions or other protocol modifications) should be made. If an efficacy interim analysis is specified in an ISA, the AC will also be responsible for review of the available efficacy data. The AC reviewing the interim data will include, at a minimum, a Lilly medical physician, a statistician, and a representative from the Lilly Global Patient Safety Organization, and may include Lilly study team members. Details about the AC membership, purpose, responsibilities, and operation will be described in an AC charter, which will be approved prior to the first unblinding. Investigator sites will receive information about interim analysis results only if they need to know for the safety of their study participants.

